3.1.1 Primary Analysis

We will use a mixed effects log-binomial model to determine the association between CBT treatment and moderate to severe PPSP (score of $\geq 4/10$) over 12 months post-fracture. The choice of using a PPSP score of $\geq 4/10$ for the primary analysis was based on scores of less than 4 being defined as 'mild' pain, and so less important to patients. Prevalence of moderate to severe PPSP will be our dependent variable. Only the highest PPSP score at each visit will be included for participants with multiple fractures. CBT treatment status, stratification variables (clinical site, sex, at least one open fracture versus no open fracture(s), and high illness beliefs [defined as Somatic Pre-Occupation and Coping [SPOC] score > 85] or medium illness beliefs [$58 < \text{SPOC score} \leq 85$] versus low illness beliefs [$\text{SPOC score} \leq 58$]), and time of assessment (continuous measure in days) will be included in the model as fixed effects, with patients entered as a random intercept. A time-by-treatment interaction term will also be added to the model, allowing the

treatment effect to vary over time. Results will be reported using marginal standardization as adjusted risk ratios (aRRs) with a 95% confidence interval (95% CI) and p-value (**Table 8**).

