3.0 ANALYSIS

3.1 Analysis Methods

The primary and secondary analyses will be conducted following intention-to-treat (ITT) principles, ensuring that participants are analyzed in their originally assigned treatment groups, regardless of adherence or protocol deviations. The date on which the participant's fracture(s) occurred will be used as the starting point for all time-to-event analyses.

We will use multiple imputations to account for missing data in the analyses and minimize potential bias under the assumption that the data are missing at random (MAR). This approach will allow for the uncertainty associated with missing values to be properly accounted for, improving the robustness of statistical inferences.⁴ Additionally, as we anticipate high rates of early withdrawal, we will account for this in the analyses, if needed.

If any of the analysis models fail to converge, we will remove adjustment covariates one by one until convergence is achieved. The same set of covariates will be used consistently across all models in the primary and secondary analyses.

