3.1.2 Secondary Analyses

- 1) *Health-Related Quality of Life (HRQoL)*: We will use linear repeated measures mixed modeling to explore the association between: 1) CBT treatment status and Short Form-36 (SF-36) Physical Component Summary (PCS) scores over 12 months, and 2) CBT treatment status and SF-36 Mental Component Summary (MCS) scores over 12 months. The SF-36 is an established, reliable and validated health status measure.⁵⁻⁷ It measures HRQoL through an 8-domain profile of functional health and well-being, physical and mental health summary measures (PCS and MCS). The SF-36 PCS and MCS are scored on a scale from 0 to 100, with 100 representing the highest level of functioning possible. SF-36 PCS and MCS scores will be included as the dependent variable in each corresponding model. CBT treatment status, stratification variables, and time of assessment (continuous measure in days) will be included in the models as fixed effects, with patients entered as a random intercept. The models will also be adjusted for baseline SF-36 PCS and MCS scores, accordingly, as well as including a time-by-treatment interaction term. Results will be reported using marginal standardization as adjusted mean differences (aMDs) with 95% CIs and p-values (**Table 8**).
- 2) *Return to Function*: We will use Cox proportional hazards regression modeling to explore the association between: 1) CBT treatment status and returning to $\geq 80\%$ of pre-injury functioning, 2) CBT treatment status and returning to full function with respect to work, 3) CBT treatment status and returning to full function with respect to leisure activities, and 4) CBT treatment status and returning to full function with respect to responsibilities around the home. These return to function components are measured using the Return to Function questionnaire, which has been used in a previous fracture trial⁸ documents when participants return to work, household activities, and leisure activities without limitations, as well as when they achieve 80% of their pre-injury function. Participants will be censored at their last documented follow-up visit. The analyses will adjust for stratification variables and the results will be reported as hazard ratios (HRs) with 95% CIs and p-values (**Table 9**).

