- 3) *Pain over Time*: We will use linear repeated measures mixed modeling to explore the association of 1) CBT treatment status and Brief Pain Inventory - Short Form (BPI-SF) Average Pain Severity scores over 12 months and 2) CBT treatment status and BPI-SF Pain Interference scores over 12 months. The BPI-SF assesses the severity of pain and its impact on function.⁹ All items are rated on a 0-10 scale, with higher scores indicating greater pain severity and interference. BPI-SF Average Pain Severity and BPI-SF Pain Interference scores will be included as the dependent variable in each corresponding model. CBT treatment status, stratification variables, and time of assessment (continuous measure in days) will be included in the models as fixed effects, with patients entered as a random intercept. The models will also be adjusted for baseline BPI-SF Average Pain Severity and BPI-SF Pain Interference scores, accordingly, as well as include a time-by-treatment interaction term. Results will be reported using marginal standardization as adjusted mean differences (aMDs) with 95% CIs and p-values (**Table 8**).

- 4) *Opioid Use*: We will use logistic regression modeling to explore the association between CBT treatment status and opioid use status. Two separate models will be created to analyze opioid use status (yes versus no) at both 6 months and 12 months. Opioid use status will be included as the dependent variable, and each model will be adjusted for stratification variables. Results will be reported as ORs with 95% CIs and p-values (**Table 8**).

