Paramedic		
Search and rescue personnel		
Military employment history		
Active duty		
Reserve/Guard		
Veteran/Retiree		
Civilian		
Highest level of education completed		
8th grade or less		
9th to 12th grade, no diploma		
General education diploma or high school graduate		
Some college, no degree		
Associates degree (2-year degree)		
Bachelors/college degree		
Some graduate work, no degree		
Graduate degree		
Professional degree		
Did not want to disclose		

	CBT n (%) (n= XX)	Usual Care n (%) (n= XX)
Current smoker		
Functional Comorbidity Index, mean (SD)		
Receiving other mental health support** Counselling Support group Other		
Receiving medication for mental health support** Antidepressant medications Antipsychotic medications Mood stabilizers Psychostimulants, stimulants Anxiolytics Central nervous system depressants Substance abuse medications Cognitive enhancers Other		
Taking pain medication in the past two weeks* * Acetaminophen (e.g., Tylenol) Opioids (e.g., oxycodone, Dilaudid) NSAIDs (e.g., ibuprofen, Aleve, naproxen) GABA Analogue (e.g., Neurontin, Lyrica) Benzodiazepines (e.g., diazepam) Cannabis Other		
Baseline SPOC Score*** Low (≤ 58) Medium ($58 < \text{SPOC score} \leq 85$) High (>85)		

*This table shows all response options for the data collected. In the primary manuscript, some data categories may be collapsed as appropriate or presented in a supplementary appendix.

**Some participants specified more than one type of mental health support/medication.

***SPOC: Somatic Pre-Occupation and Coping

Table 4: Injury Details and Fracture Characteristics*

	CBT n (%) (n= XX)	Usual Care n (%) (n= XX)
Mechanism of injury Motor vehicle accident Fall Direct trauma (penetrating) Direct trauma (blunt) Crush injury Twist injury Blast injury Ballistic injury Spontaneous		
Work-related injury		
Injury severity score, mean (SD)		
American Society of Anesthesiologists (ASA) physical class Class I or II Class III or higher		
Days from injury to admission, mean (SD)		
Duration of hospital stay (days), mean (SD)		
Fracture type Open Closed Both		
Number of included fractures per patient 1 2 3 4 5 or more		
Location of fracture Upper extremity Lower extremity Both		
AO/OTA classification 11 A-C 12 A-C 13 A-C 14 A-C 15 A-C 2R1 A-C 2R2 A-C 2R3 A-C 2U1 A-C 2U2 A-C 2U3 A-C	N=XX fractures	N=XX fractures

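### The primary pain model and the two opioid models leave out baseline pain and baseline opioid use, although both are collected; this costs efficiency but does not bias the randomised comparison

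*SAP*

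**What the plan says.** **Primary model (SAP 3.1.1).** "We will use a mixed effects log-binomial model to determine the association between CBT treatment and moderate to severe PPSP", defined as a score of at least 4 out of 10. The fixed effects start with "CBT treatment status, stratification variables (clinical site, sex, at least one open fracture versus no open fracture(s". They continue with SPOC illness-belief category, time in days and a time-by-treatment interaction; patient is a random intercept. The result is standardised: "Results will be reported using marginal standardization as adjusted risk ratios (aRRs) with a 95% confidence interval (95% CI) and p-value".

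**Opioid models (SAP 3.1.2, item 4).** There are two logistic regressions, at 6 and at 12 months. "Opioid use status will be included as the dependent variable, and each model will be adjusted for stratification variables". They are reported as odds ratios.

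**Models that do adjust for baseline (SAP 3.1.2, items 1 and 3).** For quality of life: "The models will also be adjusted for baseline SF-36 PCS and MCS scores, accordingly". For pain severity and interference: "The models will also be adjusted for baseline BPI-SF Average Pain Severity and BPI-SF Pain Interference scores, accordingly".

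**Availability.** The second of these quotes shows that baseline BPI-SF is collected. Table 3 lists "Opioids (e.g., oxycodone, Dilaudid") among pain medications taken in the two weeks before baseline. Table 7 lists the PPSP form at 3, 6, 9 and 12 months, and no baseline PPSP score is described anywhere.

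**General rule (SAP 3.1).** If a model fails to converge, covariates are removed one at a time, in no stated order. Then: "The same set of covariates will be used consistently across all models in the primary and secondary analyses".

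**The concern.** Pain reported at enrolment is likely to predict pain over the following year, and opioid use at enrolment is likely to predict opioid use at 6 and 12 months. The SAP uses baseline scores for its continuous repeated-measures outcomes but not for the primary pain outcome or for opioid use, and it gives no reason. The secondary analysis of BPI-SF pain therefore uses information that the primary analysis of a closely related construct does without.

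At stake is power for the primary comparison, and for opioid use. The subgroup and sensitivity models follow the primary model and so inherit the omission. In the adherence analyses of section 3.3, item 3, participants in the CBT arm are selected after randomisation, so baseline pain could also confound. That is a further reason to carry the term into the copied models.

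Read literally, the section 3.1 sentence on one covariate set for all models also does not fit models that each add their own baseline score.

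**Working it through.** The SAP states no sample size, power, prevalence, effect size or correlation, so there is no figure of its own to reproduce. Everything below rests on assumed inputs.

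**1. Single visit, by formula.** Let r be the correlation of baseline pain with latent follow-up pain and p the prevalence. The share of outcome variance explained is R² = (r·φ(z_p))² / [p(1−p)], and the variance of a standardised contrast falls by about R².
- Example: r = 0.4, p = 0.4, φ(z_p) = 0.386. R² = (0.4 × 0.386)² / 0.24 = 0.10.
- Over r = 0.3 to 0.6 and p = 20% to 50%, R² runs from about 0.04 to 0.23.

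**2. Four visits, simulated, without SPOC in the model.** Two set-ups were used: 600 participants with modified Poisson regression and cluster-robust errors, and 800 participants with regression of person means. Both give variance reductions of about 10%, 17% and 27% at r = 0.3, 0.4 and 0.5.

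**3. Four visits, with SPOC in both models.** This is closer to the plan, because SPOC category is a stratification variable. Assumptions: 600 participants, control prevalence 38%, SPOC in thirds, SPOC correlated about 0.35 with the outcome and 0.4 with baseline pain. The fits used cluster-robust errors in place of the plan's random intercept.

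| r | Variance reduction | Equivalent extra participants, 1/(1−reduction) − 1 | Power, if 80% without baseline pain |
|---|---|---|---|
| 0.3 | 5% | 1/0.95 − 1 = 5% | 82% |
| 0.4 | 12% | 1/0.88 − 1 = 14% | 85% |
| 0.5 | 21% | 1/0.79 − 1 = 27% | 88% |

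Power is Φ((1.96 + 0.84)/√(1 − reduction) − 1.96). At r = 0.4 this is Φ(2.80/0.938 − 1.96) = Φ(1.03) = 0.85. Repeat runs agree to within one or two percentage points, and the log risk ratio hardly moves.

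**4. Convergence.** A continuous predictor under a log link can push fitted risks above 1.
- In the set-up of step 3, this happened in 3%, 85% and 100% of replicates at r = 0.3, 0.4 and 0.5.
- A plain log-binomial fit without a random intercept (50 replicates per setting) never failed without baseline pain. With it, the fit failed in 0%, 24% and 66% of replicates.
- At 55% prevalence the failures with baseline pain were 16%, 56% and 92%.
- Standardising from a logistic model instead kept the gain (5%, 13% and 23%), with essentially the same log risk ratio.

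**5. Opioid models.** Simulation with 800 participants and a conditional odds ratio of 0.5. Scenarios give baseline use, then later use in the control arm among baseline users and non-users.

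| Scenario | Log OR, strata-type model → with baseline use | SE | Absolute log OR / SE | Power |
|---|---|---|---|---|
| 50%; 25% v 5% | −0.654 → −0.699 | 0.230 → 0.237 | 2.84 → 2.95 | 81% → 85% |
| 50%; 35% v 5% | −0.621 → −0.699 | 0.200 → 0.212 | 3.11 → 3.30 | 88% → 92% |
| 40%; 50% v 10% | −0.583 → −0.704 | 0.177 → 0.195 | 3.29 → 3.61 | 92% → 96% |

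The standard error rises, but the odds ratio moves further from 1 by more, so power rises by about 4 points. (The comparison model here held treatment only, with no strata.)

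**The case against.** Adjusting for stratification factors alone is a valid prespecified choice, and nothing in sections 3.1.1 or 3.1.2 is wrong as a method. Several stronger readings are tempting, and the SAP does not support them.

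- **That the primary model omits its own outcome's baseline.** No baseline PPSP score is described. PPSP is scored on its own form, and for participants with several fractures the highest score counts. BPI-SF pain is another instrument on the same 0 to 10 range. The case rests on prognostic value, not on symmetry with the SF-36 and BPI-SF models.
- **That the result is biased.** Treatment is randomised, and the confidence interval already allows for chance imbalance. Section 2.2 also promises to note clinically important imbalance.
- **That the gain is as large as a model without SPOC suggests.** SPOC category recovers part of it. Excluding fully weight-bearing patients without pain may also weaken the correlation.
- **That the opioid odds ratio loses precision.** Its standard error goes up with adjustment, and the odds ratio becomes more conditional. The gain is in power.
- **That the change is free.** It is not: the larger the gain, the likelier it is that the log-binomial model fails and the SAP's own rule starts to remove covariates.

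The last objection carries the most weight. It argues for a better fallback rather than for leaving out a likely strong predictor, since a standardised logistic model keeps the gain.

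**Conclusion.** The point holds as a loss of efficiency that can be recovered cheaply. The omissions and the availability of both baseline variables are plain from the SAP. The size is not: it depends on assumed sample size, prevalence and correlations. With SPOC in the model, a variance reduction of about 5% to 21% for the primary log risk ratio is a fair range for correlations of 0.3 to 0.5. For opioid use the gain is about 4 points of power in the scenarios tried.

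The randomised comparison stays valid either way. The section 3.1 sentence on a common covariate set needs a wording change. Since it follows the convergence rule, it may have been meant only for covariates removed under that rule, but it does not say so.

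**What to change.** Make these changes before outcome data are seen by treatment group:

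1. **Primary model (3.1.1).** Add continuous baseline BPI-SF Average Pain Severity as a fixed effect. Carry it into the subgroup models (3.2) and the sensitivity and exploratory models (3.3) that follow the primary method.
2. **Convergence (3.1).** State that if the log-binomial model does not converge, the risk ratio is obtained by marginal standardisation from a mixed logistic model, or from modified Poisson regression with robust standard errors. Baseline pain is retained in either case and not dropped. For the mixed logistic model, say that standardisation averages over the random intercept.
3. **Opioid models (3.1.2, item 4).** Add baseline opioid use (yes or no) to both. Report a marginally standardised risk ratio or risk difference, choose which now, and change the footnotes of Tables 8 and 12 to match.
4. **Common covariate set (3.1).** Reword to allow outcome-specific baseline terms in addition to the shared covariates.

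The cost is SAP wording and some programming. No new data are needed, and missing baseline values can go into the planned multiple imputation. The one real downside is the higher risk of log-binomial non-convergence, which the second change deals with.

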3.1.2 Secondary Analyses

- 1) *Health-Related Quality of Life (HRQoL)*: We will use linear repeated measures mixed modeling to explore the association between: 1) CBT treatment status and Short Form-36 (SF-36) Physical Component Summary (PCS) scores over 12 months, and 2) CBT treatment status and SF-36 Mental Component Summary (MCS) scores over 12 months. The SF-36 is an established, reliable and validated health status measure.⁵⁻⁷ It measures HRQoL through an 8-domain profile of functional health and well-being, physical and mental health summary measures (PCS and MCS). The SF-36 PCS and MCS are scored on a scale from 0 to 100, with 100 representing the highest level of functioning possible. SF-36 PCS and MCS scores will be included as the dependent variable in each corresponding model. CBT treatment status, stratification variables, and time of assessment (continuous measure in days) will be included in the models as fixed effects, with patients entered as a random intercept. The models will also be adjusted for baseline SF-36 PCS and MCS scores, accordingly, as well as including a time-by-treatment interaction term. Results will be reported using marginal standardization as adjusted mean differences (aMDs) with 95% CIs and p-values (**Table 8**).
- 2) *Return to Function*: We will use Cox proportional hazards regression modeling to explore the association between: 1) CBT treatment status and returning to $\geq 80\%$ of pre-injury functioning, 2) CBT treatment status and returning to full function with respect to work, 3) CBT treatment status and returning to full function with respect to leisure activities, and 4) CBT treatment status and returning to full function with respect to responsibilities around the home. These return to function components are measured using the Return to Function questionnaire, which has been used in a previous fracture trial⁸ documents when participants return to work, household activities, and leisure activities without limitations, as well as when they achieve 80% of their pre-injury function. Participants will be censored at their last documented follow-up visit. The analyses will adjust for stratification variables and the results will be reported as hazard ratios (HRs) with 95% CIs and p-values (**Table 9**).
- 3) *Pain over Time*: We will use linear repeated measures mixed modeling to explore the association of 1) CBT treatment status and Brief Pain Inventory - Short Form (BPI-SF) Average Pain Severity scores over 12 months and 2) CBT treatment status and BPI-SF Pain Interference scores over 12 months. The BPI-SF assesses the severity of pain and its impact on function.⁹ All items are rated on a 0-10 scale, with higher scores indicating greater pain severity and interference. BPI-SF Average Pain Severity and BPI-SF Pain Interference scores will be included as the dependent variable in each corresponding model. CBT treatment status, stratification variables, and time of assessment (continuous measure in days) will be included in the models as fixed effects, with patients entered as a random intercept. The models will also be adjusted for baseline BPI-SF Average Pain Severity and BPI-SF Pain Interference scores, accordingly, as well as include a time-by-treatment interaction term. Results will be reported using marginal standardization as adjusted mean differences (aMDs) with 95% CIs and p-values (**Table 8**).

- 4) *Opioid Use*: We will use logistic regression modeling to explore the association between CBT treatment status and opioid use status. Two separate models will be created to analyze opioid use status (yes versus no) at both 6 months and 12 months. Opioid use status will be included as the dependent variable, and each model will be adjusted for stratification variables. Results will be reported as ORs with 95% CIs and p-values (**Table 8**).

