2.4 Outcome Completion Rates

We will report on the outcome completion rates at each follow-up visit. The data will be presented as frequencies and percentages (**Table 7**).

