31 A-C 32 A-C 33 A-C 34 A-C 41 A-C 42 A-C 43 A-C 4F1 A-C 4F2 A-C 4F3 A-C 44 A-C 61 A-C 62 A-C 71 A-C 72 A-C 73 A-C 74 A-C 75 A-C 76 A-C 77 A-C 78 A-C 79 A-C 81 A-C 82 A-C 83 A-C 84 A-C 85 A-C 86 A-C 87 A-C 88 A-C 89 A-C		
Severe soft tissue injury for closed fractures Extensive skin contusion or crush injury Severe damage to underlying muscle Compartment syndrome Degloving	N=XX closed fractures	N=XX closed fractures
Type of internal fixation Intramedullary nail Plate(s) and adjacent screws Screw(s) alone K-wire(s) Cerclage Other	N=XX fractures	N=XX fractures

*This table shows all response options for the data collected. In the primary manuscript, some data categories may be collapsed as appropriate or presented in a supplementary appendix.

Table 5: CBT Compliance (n=XX)

	Number of CBT Modules Completed							
	None n (%)	1 n (%)	2 n (%)	3 n (%)	4 n (%)	5 n (%)	6 n (%)	7 n (%)
All Participants Randomized to CBT								
Sex								
Male								
Female								
Fracture Type								
Any open fracture								
No open fracture								
Background/Employment								
Military, veteran, and first responder								
Not a veteran, first responder or employed by the military								
SPOC Score								
Low (≤ 58)								
Medium ($58 < \text{SPOC score} \leq 85$)								
High (>85)								
Site Location								
Canada								
United States								
Age								
<60								
≥ 60								
Injury Severity Score								
<9								
≥ 9								

Table 6: CBT Compliance (Condensed to Categories) (n=XX)

	Number of CBT Modules Completed			
	None n (%)	1-3 n (%)	4-6 n (%)	7 n (%)
All Participants Randomized to CBT				
Sex				
Male				
Female				
Fracture Type				
Any open fracture				
No open fracture				
Background/Employment				
Military, veteran, and first responder				
Not a veteran, first responder or employed by the military				
SPOC Score				
Low (≤ 58)				
Medium ($58 < \text{SPOC score} \leq 85$)				
High (>85)				
Site Location				
Canada				
United States				
Age				
<60				
≥ 60				
Injury Severity Score				
<9				
≥ 9				

Table 7: Outcome Completion Rates at Follow-up Visits (N=XX total sample size)

Outcome	3 months n (%)	6 months n (%)	9 months n (%)	12 months n (%)
PPSP Form				
SF-36 Form				
Return to Function Form				
BPI-SF Form				
Opioid Class Medication Question				

Table 8: Impact of CBT versus Usual Care on Primary and Secondary Outcomes

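### Return-to-function times are censored at the last documented visit rather than the last completed Return to Function item, so unassessed time can count as not yet returned; a minor correction to secondary endpoints

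*SAP*

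**What the plan says.** Section 3.1.2, item 2, covers four milestones: at least 80% of pre-injury function, and full return to work, to leisure and to home responsibilities. The model is stated as "We will use Cox proportional hazards regression modeling to explore the association between" treatment and each of these. The source of the event times is stated too: "These return to function components are measured using the Return to Function questionnaire". The item adds that the form records when each milestone was reached, and it names no other source. The censoring rule then follows: "Participants will be censored at their last documented follow-up visit". Section 3.1 fixes the origin: "The date on which the participant's fracture(s) occurred will be used as the starting point for all time-to-event analyses".

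Section 2.4 says "We will report on the outcome completion rates at each follow-up visit". Its Table 7 has columns for 3, 6, 9 and 12 months and gives "Return to Function Form" its own row, apart from the PPSP, SF-36, BPI-SF and opioid rows. The table is laid out for the total sample, not by arm.

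On missing data, section 3.1 says "We will use multiple imputations to account for missing data in the analyses". It does not say how imputation would apply to event times or censoring dates.

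**The concern.** A censoring date should be the last time at which the event status was known. Here status is known only through the Return to Function questionnaire, while the rule uses the visit. Suppose a participant last completes the form at 6 months, had not returned to work by then, and answers only the pain items at 12 months. The rule censors this person at 12 months, so 12 − 6 = 6 months enter the Cox risk set as event-free without having been assessed. A return in that window is never counted.

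This lowers the apparent return rate in whichever arm has more such visits. If that is the CBT arm, a real benefit is understated. If it is usual care, a benefit is exaggerated or created. All four HRs in Table 9, which serve the secondary objective on faster return to function, would be affected. The planned outputs would not reveal it: Table 7 is not split by arm, Table 9 shows only HRs and p-values, and the available-case analysis in Table 12 has no return-to-function row.

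**Working it through.** The SAP gives no HR, event count or form-completion rate for this endpoint, so there is no planned figure to reproduce. The check is of direction and size.

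**Inputs from the SAP.** Visits at 3, 6, 9 and 12 months; event times from the form only; censoring at the last visit.

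**Assumptions, not in the SAP.** Exponential return times with a median of 9 months. All participants attend to 12 months. A fraction q stop completing this form after month 3, 6 or 9 (one third each) while other forms continue. Stopping is unrelated to recovery.

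**Step 1, hazard and cumulative return.** λ = ln 2 / 9 = 0.0770 per month. F(k) = 1 − exp(−λk) gives F(3) = 0.206, F(6) = 0.370, F(9) = 0.500, F(12) = 0.603. The mean over months 3, 6 and 9 is 0.359.

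**Step 2, recorded events per participant.** E(q) = (1 − q) × 0.603 + q × 0.359.

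**Step 3, person-time.** Assessed time to month k is F(k)/λ: 7.831 months for those who continue and, on average, 4.659 for those who stop. The visit rule adds unassessed time (1 − F(k)) × (12 − k): 0.794 × 9 = 7.143, 0.630 × 6 = 3.780 and 0.500 × 3 = 1.500, mean 4.141. So P(q) = (1 − q) × 7.831 + q × (4.659 + 4.141).

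**Step 4, apparent return rate E/P.**

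| q | E | P (months) | E/P |
|---|---|---|---|
| 5% | 0.591 | 7.880 | 0.0750 |
| 10% | 0.579 | 7.928 | 0.0730 |
| 20% | 0.554 | 8.025 | 0.0691 |
| 30% | 0.530 | 8.122 | 0.0652 |

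The true rate is 0.0770 in every row. Without the 4.141 months of unassessed time, E/P returns to 0.0770 for every q.

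**Step 5, ratio between arms when the true HR is 1.00.** The second column is the ratio of rates from step 4. The third is a simulated Cox HR (200,000 per arm, four replicates) in which the form is missed independently at each visit, so that a later form can fill an earlier gap.

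| Non-completion, CBT vs usual care | Permanent stop | Intermittent misses |
|---|---|---|
| 10% vs 5% | 0.97 | 0.99 |
| 20% vs 10% | 0.95 | 0.97 |
| 30% vs 10% | 0.89 | 0.93 |

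A Cox simulation of the permanent-stop pattern agreed with the hand calculation to within 0.004. Swapping the arms inverts the ratios.

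**Step 6, a true effect.** At a true HR of 1.30 the visit rule gave 1.22 to 1.26 at 20% versus 10%, and 1.16 to 1.20 at 30% versus 10%. Censoring at the last completed form gave 1.30 in each case.

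**Step 7, equal completion.** At 10%, 20% or 30% in both arms there was no bias at HR 1.00. At HR 1.30 the attenuation was about 1% or less (1.29 to 1.30).

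**Step 8, a harsher pattern.** A separate simulation let some participants never complete the form, with 5% dropout per visit and 50% or 70% return by 12 months in usual care. At true HR 1.00 it gave 0.95 to 0.96, 0.92 to 0.93 and 0.84 to 0.86 for the three contrasts. With equal non-completion and a true HR of 1.25, the lowest value was 1.22.

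**The case against.** The strongest reply is that the sentence sits inside the Return to Function item, directly after the questionnaire is described, so a documented visit may simply mean one at which return-to-function status was recorded. That reading is possible, and under it the proposed wording only makes the intent explicit. The text does not say so, however, and two programmers could derive different censoring dates from the same data.

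Second, the general imputation sentence might be said to cover missing forms. It does not say how, and once a participant is assigned a censoring date no value is visibly missing.

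Third, the form records when return occurred, so a later form repairs an earlier gap. This stands: only time after the last completed form is affected, and the intermittent column above is correspondingly milder.

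Two stronger readings are tempting but are not supported. A reader might infer that the CBT arm will lose more forms because high early withdrawal is anticipated. Section 3.1 names no arm, and the footnote to Figure 1 says participants were followed whatever number of sessions they completed. Those who leave the trial entirely have the same last visit and last form, so they are unaffected. A reader might also infer from Table 7 that forms are expected to diverge within a visit. A separate row per instrument is routine reporting: it allows for divergence but does not predict it.

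**Conclusion.** The point holds as a conditional one. The rule is tied to the visit while the event is known only from the form, and nothing else in the SAP closes that gap. Bias of any consequence requires that completion of this form at attended visits differs by arm. On the assumed patterns it is about 2% for a 5-point difference, 3% to 5% for 20% versus 10%, and 7% to 11% for 30% versus 10%. It is larger (up to about 16%) only if some participants never complete the form.

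The SAP gives no basis for any of these rates, so the actual size and direction are unknown. It would be wrong to conclude that the reported HRs will be biased, or biased against CBT. The figures also rest on constant hazards and on form completion being unrelated to recovery. Only secondary endpoints are involved, and severity is minor.

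**What to change.** Replace the censoring sentence in section 3.1.2, item 2, with: *Participants without a recorded return date for a milestone are censored at the last visit at which the Return to Function item for that milestone was completed.* State in the same place whether multiple imputation applies to these endpoints. Splitting Table 7 by arm would show whether completion differed.

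The cost is one sentence, one line of derivation code and slightly less person-time. A participant who never completes the item would contribute no follow-up time, so the number affected in each arm should be reported. The new rule still assumes that stopping the form is not informative about recovery. If people stop answering because they have recovered, censoring at the last completed item is biased too.
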